## 14.2.5.4. Reporting Requirements

#### 14.2.5.4.1. Serious Adverse Reporting Requirements

Each AE is to be assessed to determine if it meets the criteria for an SAE. If an SAE occurs, expedited reporting will follow local and international regulations, as appropriate.

If an SAE occurs, the sponsor is to be notified within 24 hours of awareness of the event by the investigator. In particular, if the SAE is fatal or life-threatening, notification to the sponsor must be made immediately, irrespective of the extent of available AE information. This timeframe also applies to additional new information (follow-up) on previously forwarded SAE reports as well as to the initial and follow-up reporting of Exposure in Utero cases (Section 14.2.5.3).

In the rare event that the investigator does not become aware of the occurrence of an SAE immediately (eg, if an outpatient study patient initially seeks treatment elsewhere), the investigator is to report the event within 24 hours after learning of it and document the time of his/her first awareness of the AE.

To report the SAE, complete the SAE form electronically in the eCRF for the study. When the form is completed, will be notified electronically and will retrieve the form. If the event meets serious criteria and it is not possible for you to access the internet, fax a paper copy to the series of the series and it is not possible for you to access the internet, fax a paper copy to the series of the series o

SAE reporting on a 24-hour basis. Incoming reports are reviewed during normal business hours."

For all SAEs, the investigator is obligated to pursue and provide information to the sponsor in accordance with the timeframes for reporting specified above. In addition, an investigator may be requested by the sponsor to obtain specific additional follow-up information in an expedited fashion. This information may be more detailed than that captured on the AE page of the eCRF. In general, this will include a description of the AE in sufficient detail to allow for a complete medical assessment of the case and independent determination of possible causality. Information on other possible causes of the event, such as concomitant medications and illnesses must be provided. In the case of a patient death, a summary of available autopsy findings must be submitted as soon as possible to the sponsor or its designated representative.

### 14.2.5.5. Non-Serious Adverse Event Reporting Requirements

All AEs will be reported on the Adverse Event page(s) of the eCRF. It should be noted that the form for collection of SAE information is not the same as the Adverse Event eCRF. Where the same data are collected, the forms must be completed in a consistent manner. For example, the same AE term should be used on both forms. Adverse events should be reported using concise medical terminology on the eCRFs as well as on the form for collection of SAE information.

A non-serious AESI will be promptly entered in the eCRF and reported on expedited basis (within 24 hours) to the sponsor (or designee) to facilitate real-time review of patterns of toxicity. Investigators are to report AESIs in accordance with the SAE reporting process noted in Section 14.2.5.4.1 within 24 hours of becoming aware of all AEs of Special Interest. All AESIs must be promptly assessed by the Medical Monitor within 24 hours of receipt.

#### 14.2.5.6. Sponsor Reporting Requirements to Regulatory Authorities

Adverse events reporting, including serious unexpected serious adverse reactions (SUSAR), will be carried out in accordance with applicable local regulations.

## 15. STATISTICS

## 15.1. Sample Size

The Part 1 sample size was derived empirically from experience with previous single ascending dose clinical studies in other disorders and is deemed appropriate to achieve the study objectives.

The Part 2 sample size was selected to ensure adequate power for detecting treatment-related change in bilateral UEMS (Score from 0 to 50).

A 5-point difference, between the treated and placebo groups, in the change from baseline to 6 months in bilateral UEMS is considered clinically meaningful. Analysis of historical data for cervical SCI patients for the period between ~6-12 months following acute SCI indicates a standard deviation of bilateral UEMS change over 6 months to be around 3 to 4 points.

With a sample size of 12 subjects per active and placebo group, Part 2 of the study has 80% power with Type I error of  $\alpha$ =0.05 (two sided), assuming a 5-point difference as indicated above, and with a common standard deviation within each treatment group of approximately 4 in the change from baseline to 6 months in bilateral UEMS.

Accounting for uncertainties in the assumptions based upon historical data used to extrapolate for estimating the sample size in this study and the need for estimation of missing data a sample size of approximately 16 subjects per treatment arm (32 total) will be randomized.

## 15.2. Stages of Analysis

The analysis for this study will be performed in three stages, with the first analysis performed upon completion of the clinical portion of Part 1, the second analysis (including the core efficacy assessment) performed upon completion Day 169 of Part 2 (ie, after all subjects have completed through Study Day 169), and the final analysis performed upon completion of the post-treatment follow-up phase of Part 2 (Day 253). The methods applied to each analysis will be consistent with the objectives of the study.

The blind will be maintained for all blinded study personnel (including investigators and subjects) through the completion of Day 169 of Part 2. After completion of Day 169, designated sponsor staff and external consultants/contractors required to perform the analysis will be unblinded to the treatment allocations in order to complete data analysis though Day 169. The blind will be maintained for site investigators and subjects through completion of Day 253 unless the blind must be broken sooner for safety or regulatory reasons.

## 15.3. General Methods

Data will be tabulated using both descriptive and inferential statistics where specified.

- For Part 1, data will be tabulated by dosing cohort as well as pooled (all subjects combined), and no inferential statistics are planned.
- For Part 2, data will be tabulated for each treatment group separately (placebo and AXER-204) to allow for visual inspection of outcomes between the arms. Inferential comparison of the treatment groups is planned.

For both Parts, all data collected will be included in by-domain data listings, sorted by subject number and time point, or as appropriate.

No hypothesis testing will be performed for demographics, background, or safety data.

Continuous data will be summarized by presenting the number of subjects (n), means, mean changes from baseline, mean % changes from baseline (where appropriate), standard deviations, minimum, First quartile (Q1), median, third quartile (Q3), and maximum values. The number of subjects with missing data will be indicated.

Categorical data will be summarized by presenting the number of subjects (n), the number of subjects with missing data as well as counts and percentages in each of the categories. Percentages will be based upon the number of subjects with available data.

When inferential testing is applied to all efficacy assessments, dichotomous/binary categorical efficacy endpoints will be assessed via a 2-sided Fisher's Exact test or Chi-square test as appropriate. Continuous efficacy endpoints will also present least-squares means and p-values from hypothesis testing of efficacy endpoints using mixed-effects model for repeated measures (MMRM).

Additional details will be included in the statistical analysis plan (SAP) which will be finalized prior to unblinding Part 2 of the study and any amendments to it made prior to locking the database and unblinding the study.

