#### 7.1.2.2. Treatment Phase

Eligible subjects will be randomized to either AXER-204 or to placebo. The randomization will be stratified based on pre-treatment AIS grade (AIS A,B vs. AIS C,D) and prior receipt of study drug in Part 1 (Received AXER-204 in Part 1 vs. Did not receive AXER-204 in Part 1).

Subjects will undergo baseline assessments and receive their assigned (double-blind) treatment on Study Day 1. Study personnel will conduct telephone call with subjects on Study Day 8 ( $\pm$  3 days) to assess status regarding any adverse events. Subjects will then return to the Clinic on Day 21 ( $\pm$  5 days) for safety, efficacy, and PK assessments and their second dose of study investigational product. Thereafter, subjects will return approximately every 21 days, at Study Days 42 ( $\pm$  5 days) (third dose), 63 ( $\pm$  5 days) (fourth dose), 84 ( $\pm$  5 days) (fifth dose), 104 ( $\pm$  5 days) (sixth dose), for safety, efficacy, and PK assessments (pre-dose) and investigational product administration.

Cerebrospinal fluid samples will be collected pre-dose at each treatment (dosing) visit, including Study Day 1, during a single LP procedure for collecting and dosing. Serum for PK and immunogenicity (ADA) testing will be collected pre-dose at specified visits (See Table 11), within 4 hours prior to investigational product administration. Serum will also be collected for PK at 4 h post-dose at specified visits.

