## 15.7. Alpha Level Considerations

All inferential testing will be performed using two-sided 5% Type I error ( $\alpha$ ), and therefore 2-sided p-values  $\leq 0.05$  will be considered statistically significant in this study.

The first hypothesis test will be the key secondary efficacy endpoint of change in bilateral UEMS from baseline to Study Day 169 using the MMRM model as detailed below. Additional secondary efficacy endpoints tested will be the change in GRASSP prehension performance from baseline to Study Day 169 and of change in SCIM self-care from baseline to Study Day 169.

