## 15.10. Efficacy Endpoints

For Part 1 efficacy, outcomes will be presented by each dosing cohort, with no inferential assessments among cohorts planned. Thus, for Part 1, efficacy will be presented only descriptively.

For Part 2, changes from pre-treatment to each on-treatment time point will be calculated, with the primary time point at Day 169. Shifts over time in ordinal endpoints will be presented, with comparisons between treatment groups assessed using a CMH row mean scores statistic at each time point. Slope of change will also be evaluated. Part 2 efficacy analysis is described in the following sections.

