3.1.2.4.5 Population-level Summary for Comparison between Treatment Conditions

The treatment effect will be the difference between AXER-204 and placebo in percentages of PGIC responder rate at Study Day 169 as estimated through a Fisher's Exact Test as defined in section 8.5.2.2.

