8.5.2.1 Primary Efficacy Endpoint and Primary Efficacy Analysis

The primary efficacy endpoint is the change from baseline in bilateral UEMS to Study Day 169.

The null and alternative hypothesis for this endpoint are as follows:

 $H_0: \mu_A = \mu_P$

H_A: μ_A≠ μ_P

Where H_0 and H_A refer to the Null and alternative hypothesis to be tested, μ_A and μ_P refers to the mean change in bilateral UEMS from baseline to Study Day 169 for subjects randomized to AXER-204 and Placebo groups, respectively.

Primary analysis to compare the change from baseline in bilateral UEMS to Study Day 169 will be based upon a mixed-effects model for repeated measures (MMRM) using the mITT.

The MMRM model will include treatment (AXER-204 vs. Placebo), all post-baseline visits up until Study Day 169 (Study day 21, 63, 104, and 169), treatment-by-visit interaction, AIS grade (A, B vs C, D), and prior receipt of study drug in Part 1 (yes vs. no) as the fixed categorical effects, the baseline bilateral UEMS measurement as a covariate, and treatment-by-baseline UEMS interaction.

An unstructured covariance structure will be used to model the within-patient errors. If this analysis fails to converge, the following covariance structures will be tested in order, and the first covariance structure that converges will be used:

- toeplitz with heterogeneity (TOEPH)
- autoregressive with heterogeneity (ARH(1))
- compound symmetry with heterogeneous variances (CSH)
- toeplitz (TOEP)
- autoregressive (AR(1))
- compound symmetry without heterogeneous variances (CS)

The Kenward-Roger approximation will be used to estimate denominator degrees of freedom. Significance tests will be based on LS Means using Type III sum of squares.

Based on the MMRM, analysis of comparisons between treatment groups at each post-randomization visit will be performed. The primary analysis will be to compare

CONFIDENTIAL

treatment effect at Study Day 169. The adjusted means for each treatment group and the estimated treatment differences for the treatment comparisons will be presented for each post-randomization visit together with 95% confidence intervals for the differences and p-values for the treatment comparisons. The adjusted means and estimated treatment differences for the treatment comparisons will also be plotted, with corresponding 95% confidence intervals.

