8.5.2.2 Secondary Efficacy Endpoints

- For Change from baseline in GRASSP Bilateral PP total score to Study Day 169, analysis will be conducted using the same methodology as that used for the primary efficacy endpoint (sections 8.5.2.1 and 8.5.2.1.1).
- For Change from baseline in SCIM III Self Care score to Study Day 169, analysis will be conducted using the same methodology as that used for the primary efficacy endpoint (sections 8.5.2.1 and 8.5.2.1.1).
- Fisher's exact test at two-sided significance level 0.05 will be used to test if there is a difference of PGIC responses (1=`Much worse', 2=`Worse', 3=` A little worse', 4=`No change', 5=`A little better', 6=`Better, 7=`'Much better') at Study Day 169 between patients in treatment group and control group. In addition, Fisher's exact test to compare responder rate (proportion of patient in mITT Analysis set with responses of `A little better', `Better', or `Much better') at Study Day 169 between the two treatment groups will conducted. A descriptive table summarizing number and percentage of patients for each of the seven above responses by visit and treatment group will be created.

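### The PGIC and CGIC responder tests pool over the two randomisation strata that the MMRM endpoints adjust for, which costs power if the strata predict response

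*Protocol*

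**What the plan says.** **Design.** Protocol 7.1.2.2 states: "The randomization will be stratified based on pre-treatment AIS grade (AIS A,B vs. AIS C,D". The second factor is prior receipt of AXER-204 in Part 1, so there are 2 x 2 = 4 strata.

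**Continuous endpoints.** The model in SAP 8.5.2.1 has "AIS grade (A, B vs C, D), and prior receipt of study drug in Part 1 (yes vs. no) as the fixed categorical effects". SAP 8.5.2.2 applies the same model to GRASSP prehension performance and SCIM III self-care.

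**Responder endpoints.** Protocol 15.3 leaves a choice: "dichotomous/binary categorical efficacy endpoints will be assessed via a 2-sided Fisher's Exact test or Chi-square test as appropriate". The SAP makes that choice. For PGIC, 8.5.2.2 specifies "Fisher's exact test to compare responder rate", and the estimand in 3.1.2.4.5 is a difference in responder percentages "as estimated through a Fisher's Exact Test as defined in section 8.5.2.2". The seven-level PGIC comparison is also a Fisher test with no strata. SAP 8.5.2.3 does the same for CGIC. The two PGIC sensitivity analyses in 8.5.2.2.1 repeat the test in the per-protocol set and with discontinued subjects set to *no change*. Neither is stratified.

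**Level.** Protocol 15.7: "All inferential testing will be performed using two-sided 5% Type I error".

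**The concern.** Three of the four primary and secondary efficacy endpoints are adjusted for the randomisation factors. The fourth, PGIC, is not, and no reason is given. SAP 8.5.2.1.3 lists both factors among the subgroups it regards as possibly prognostic.

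Stratified randomisation tends to equalise the strata between arms. A pooled 2x2 table ignores this and counts between-stratum differences in response as chance variation. The reference distribution is then too wide, so the test rejects less often than it could. At stake is sensitivity on the only secondary endpoint that records the patient's own overall judgement, in a trial of about 16 per arm.

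**Working it through.** **The plan's own figure.** The only power statement concerns UEMS: 12 per arm for 80% power at a difference of 5 and SD of 4. It reproduces. The noncentrality is 5/(4 x sqrt(2/12)) = 3.06 on 22 df, which gives 83.3%; 11 per arm gives 79.6%. No power, response rate or stratum size is given for PGIC or CGIC, so those inputs below are assumptions.

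**Inputs from the documents.** 16 per arm, two-sided 5%, four strata.

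**Assumed inputs.** Stratum sizes of 6/5/3/2 in each arm; a common within-stratum log odds ratio of 2.0 (odds ratio e^2 = 7.39); placebo response rates as in the table. Active response is p1 = 7.39 p0 / (1 - p0 + 7.39 p0). For example, p0 = 15% gives 1.108/1.958 = 56.6%.

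**The two tests.**
- *Pooled Fisher.* Given m responders among 32, the number X on AXER-204 has P(X = x) = C(16,x) C(16,m-x) / C(32,m).
- *Exact stratified.* X_k is hypergeometric within stratum k given that stratum's responders, and the statistic is the sum of the X_k. Its null distribution is the convolution of the stratum distributions.
- In both, the two-sided p-value sums all outcomes no more probable than the one observed, and the test rejects at p <= 0.05.

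**Why pooling costs power.** As an illustration, take two strata of 8 per arm, with 2 of 16 and 10 of 16 responding.
- Pooled null variance: 16 x 16 x 12 x 20 / (32^2 x 31) = 1.94.
- Stratified: 8 x 8 x 2 x 14 / (16^2 x 15) + 8 x 8 x 10 x 6 / (16^2 x 15) = 0.47 + 1.00 = 1.47.
- With 6 of 16 responding in each stratum, the stratified variance is 1.00 + 1.00 = 2.00, so nothing is gained.

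**Power, balanced strata, log odds ratio 2.0 (simulated).**

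| Placebo response by stratum | Pooled Fisher | Exact stratified | Difference |
|---|---|---|---|
| 30% in all (none) | 64.5% | 65.3% | 0.8 |
| 20/40/25/50% (mild) | 59.2% | 61.8% | 2.6 |
| 15/50/30/70% (moderate) | 46.9% | 54.0% | 7.1 |
| 10/60/20/80% (strong) | 31.4% | 45.6% | 14.2 |

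Exact enumeration of the same cases agrees within 0.4 points. Null rejection in the three cases with a stratum effect is 0.5-1.6% pooled and 1.8-2.0% stratified.

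**A second layout.** With 6/6/2/2 per arm, an odds ratio of 6 and placebo rates alternating between two values, pooled against stratified power is 55% vs 56% (30% throughout), 42% vs 47% (15/45%) and 23% vs 36% (10/60%).

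**Chance imbalance.**
- AXER-204 6/6/2/2 and placebo 7/4/3/2, moderate rates: 55% pooled, 60% stratified.
- AXER-204 6/6/1/3 and placebo 7/5/3/1, mild rates: 68.1% pooled, 63.7% stratified.

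**The case against.** The strongest reply is that the loss is hypothetical. The documents give no responder rate, overall or by stratum. SAP 3.1.2.1 describes enrolled subjects as functionally similar in arm and hand impairment, and SAP 2.3.2 expects little spontaneous motor change. An odds ratio of 7.39 is also large: at a log odds ratio of 1.0 the mild case is 13.6% pooled vs 16.1% stratified, low either way. All of this stands as a limit on the size of the loss.

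A second reply is that the estimand is the overall difference in percentages, which a pooled table addresses directly. That is fair, but the target does not change. With n_k per arm in stratum k, the Mantel-Haenszel weights are n_k/2, and the weighted difference equals the pooled one.

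Third, four cells in 32 subjects are sparse, and much of Fisher's conservatism is discreteness, which an exact stratified test keeps. This is also true: its null rejection is still only about 2%.

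Four stronger readings are tempting and are not supported.
- *The pooled test is invalid.* It is not. The error is on the conservative side.
- *Any unstratified test permitted by the protocol falls below 5%.* Not so for chi-square. In balanced layouts its null rejection is 5.8% with non-prognostic strata (30/30%), 5.1-5.2% at 20/40%, 4.4-4.5% at 15/45% and 2.4-2.5% at 10/60%.
- *The ordinal test in Protocol 15.10 has the same fault.* That section has "comparisons between treatment groups assessed using a CMH row mean scores statistic at each time point". It is silent on strata rather than expressly unstratified, and the SAP does not retain the test.
- *Stratifying can never cost power.* The second imbalance case above shows that it can.

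**Conclusion.** The omission is established from the text. The SAP's PGIC and CGIC responder tests ignore both randomisation factors, the MMRM endpoints use them, and no stratified sensitivity analysis fills the gap. The consequence is reduced sensitivity, not a false-positive risk.

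The size depends on how strongly AIS grade and prior AXER-204 predict the patient's or rater's impression of change. Under the assumed balanced layout the loss runs from about 1 point to about 14, and neither end can be excluded from the documents. Under chance imbalance no general direction can be claimed. This is an inexpensive improvement that matches the analysis to the design. It does not undermine the trial's conclusions.

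**What to change.** In SAP 8.5.2.2, 8.5.2.2.1 and 8.5.2.3:

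- Compare PGIC and CGIC responder rates with an exact (conditional) Cochran-Mantel-Haenszel test stratified by AIS grade (A,B vs C,D) and prior AXER-204 (yes/no).
- Report the Mantel-Haenszel stratum-weighted difference in responder percentages. This also supplies the estimate that SAP 3.1.2.4.5 calls for, since Fisher's test yields only a p-value.
- If a stratum has subjects in only one arm, collapse over prior receipt and keep AIS grade.

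Timing limits how this is presented. SAP section 10 records that Day 169 results were unblinded and reviewed before this version, with the Day 253 lock still ahead. The stratified test can therefore be specified for PGIC at Day 253, with a note that the change follows the Day 169 unblinding. At Day 169 it belongs beside the planned Fisher test as a labelled supportive analysis. CGIC has only that supportive role, because SAP 3.1.2.5.2 excludes it from the Day 253 analyses.

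The cost is a few lines of SAP text and one procedure option. Sparse strata add little information, and under some favourable chance imbalances the pooled Fisher test would have had more power.

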## 15.4. Handling of Missing Data

Every attempt will be made to collect all protocol required data at each time point.

Imputations will only be performed for efficacy data and for missing or partial dates, missing severity or relationship to investigational product. Missing AE or CM dates and missing severity or relationship to investigational product will always use a conservative approach. Details will be included in the SAP.

For subjects who discontinue treatment (for any reason), subjects will continue to be followed and key efficacy endpoints and safety data collected where possible.

The primary analyses for change in bilateral UEMS will use a mixed model repeated measures which automatically accounts for the missing data based upon the covariate structure assumed. To evaluate robustness of results, sensitivity analyses will be performed with imputation methods for missing data.

## 15.5. Subgroups

The sample size precludes analysis by-subgroup. However, exploratory assessment of any trends among subgroups (eg, by pre-treatment AIS grade) may be performed, after initial review if the data warrant.

